**In addition, the following inclusion criteria only apply to the additional population with rebound:**

5. Presenting with documented, symptomatic COVID-19 rebound within 14 days following completion of an initial 5-day treatment course with nirmatrelvir/ritonavir as specified in [Appendix 9, Section 10.9.5](#).

## **5.2. Exclusion Criteria**

Participants are excluded from the study if any of the following criteria apply:

### **Medical Conditions:**

1. Current need for hospitalization or anticipated need for hospitalization within 24h after randomization in the clinical opinion of the site investigator.
2. Known medical history of active liver disease (other than nonalcoholic hepatic steatosis), including chronic or active hepatitis B or C infection, primary biliary cirrhosis, Child-Pugh Class C, or acute liver failure.
3. History of hypersensitivity or other contraindication to any of the components of the study interventions, as determined by the investigator.
4. Suspected or confirmed concurrent active systemic infection other than COVID-19 that may interfere with the evaluation of response to the study intervention.
5. Any comorbidity requiring hospitalization and/or surgery within 7 days prior to study entry, or that is considered life threatening within 30 days prior to study entry, as determined by the investigator.
6. Receiving dialysis or have known age-specific eGFR <30 mL/min/1.73 m^2 or eCrCl <30 mL/min at screening as measured by a serum creatinine point of care device ([Appendix 7, Section 10.7](#)).
7. Oxygen saturation of <92% on room air obtained at rest within 24h prior to randomization. (See [Appendix 9, Section 10.9.6](#)).
8. Other medical or psychiatric condition including recent (within the past year) or active suicidal ideation/behavior or laboratory abnormality that may increase the risk of study participation or, in the investigator's judgment, make the participant inappropriate for the study.

### **Prior/Concomitant Therapy:**

9. Current use of any prohibited concomitant medication(s) (see [Section 6.9, Section 10.9.7, and Appendix 8](#)).

### **Prior/Concurrent Clinical Study Experience:**

10. Current or previous administration with an investigational product (drug or vaccine) within 30 days (or as determined by the local requirement) or 5 half-lives preceding the first dose of study intervention used in this study (whichever is longer).  
Authorized or products with conditional approval are not considered investigational.
11. Prior participation in this trial.

### **Other Exclusion Criteria:**

12. Females who are pregnant up to <14 weeks gestation. Pregnancy  $\geq$ 14 weeks is not exclusionary.
13. Investigator site staff directly involved in the conduct of the study and their family members, site staff otherwise supervised by the investigator, and sponsor and sponsor delegate employees directly involved in the conduct of the study and their family members.

## **5.3. Lifestyle Considerations**

### **5.3.1. Contraception**

All female participants who are not pregnant at study entry, and who in the opinion of the investigator, are biologically capable of having children must agree to use a highly effective method of contraception consistently and correctly for at least 28 days after the last study intervention.

Note: If the childbearing potential changes after start of the study (eg, a premenarchal female participant experiences menarche) or the risk of pregnancy changes (eg, a female participant who was not heterosexually active becomes active), the participant must discuss this with the investigator, who should determine if a female participant must begin a highly effective method of contraception. If reproductive status is questionable, additional evaluation should be considered.

The investigator or their designee, in consultation with the participant, will confirm that the participant is utilizing an appropriate method of contraception for the individual participant and their partner(s) from the permitted list of contraception methods (see [Appendix 4, Section 10.4.4](#)) and will confirm that the participant has been instructed in its consistent and correct use. At time points indicated in the [SoA](#), the investigator or designee will inform the participant of the need to use highly effective contraception consistently and correctly and document the conversation and the participant's affirmation in the participant's chart. Participants need to affirm their consistent and correct use of at least 1 of the selected methods of contraception, considering that their risk for pregnancy may have changed since the last visit.

In addition, the investigator or designee will instruct the participant to call immediately if the selected contraception method is discontinued and document the requirement to use an

alternate protocol-specified method, including if the participant will no longer use abstinence as the selected contraception method, or if pregnancy is known or suspected in the participant or partner.

### **5.3.2. Other Restrictions**

Participants may not participate in another interventional clinical study with an investigational compound, including those for COVID-19 therapeutics, through the long-term follow-up period. Participants who are in long-term follow-up in oncology or malignant hematology trials but who have not received investigational product within the timeline specified (see [Section 5.2](#), Exclusion Criterion #10 for timeline) are eligible for enrollment provided they meet the other eligibility criteria defined in [Section 5](#).

### **5.4. Screen Failures**

Screen failures are defined as participants who consent to participate in the clinical study but are not subsequently enrolled in the study. A minimal set of screen failure information is required to ensure transparent reporting of screen failure participants to meet the CONSORT publishing requirements and to respond to queries from regulatory authorities. Minimal information includes demography, screen failure details, and any SAE.

Individuals who do not meet the criteria for participation in this study (screen failure) may not be rescreened.

## **6. STUDY INTERVENTION(S) AND CONCOMITANT THERAPY**

Study interventions are all prespecified investigational and noninvestigational medicinal products/auxiliary medicinal products, medical devices, and other interventions (eg, surgical and behavioral) intended to be administered to the study participants during the study conduct.

For the purposes of this protocol, study intervention refers to nirmatrelvir 150 mg tablets and matching placebo and ritonavir 100 mg capsules and matching placebo.

### **6.1. Study Intervention(s) Administered**

Study intervention will be self-administered by the participant OR administered to the participant by a legal guardian or caregiver.

A legal guardian or caregiver may administer study medication. Study personnel should review dose administration requirements with the participant, as appropriate, and with the delegated caregiver(s) (may include school nurse) before administration and throughout the study as necessary.

Study Intervention(s)				
Intervention Name	Nirmatrelvir	Placebo for nirmatrelvir	Ritonavir	Placebo for ritonavir
Arm Name (group of participants receiving a specific treatment or no treatment)	nirmatrelvir/ritonavir	placebo	nirmatrelvir/ritonavir	placebo
Type	drug	placebo	drug	placebo
Dose Formulation	tablet	tablet	capsule	capsule
Unit Dose Strength(s)	150 mg	0 mg	100 mg	0 mg
Dosage Level(s)	300 mg q12h for 5 days, 10 days, or 15 days  150 mg q12h for 5 days, 10 days, or 15 days (for participants with eGFR $\geq$ 30 to <60 mL/min/1.73 m  or eCrCl $\geq$ 30 to <60 mL/min at screening)	0 mg q12h for 5 days or 10 days	100 mg q12h for 5 days, 10 days, or 15 days	0 mg q12h for 5 days or 10 days
Route of Administration	Oral	Oral	Oral	Oral
Use	Experimental	Placebo	Experimental	Placebo
IMP or NIMP/AxMP	IMP	IMP	IMP	IMP
Sourcing	Provided centrally by the sponsor.  Refer to the IPM.	Provided centrally by the sponsor.  Refer to the IPM.	Provided centrally by the sponsor.  Refer to the IPM.	Provided centrally by the sponsor.  Refer to the IPM.
Packaging and Labeling	Study intervention will be provided in blister wallets. Each	Study intervention will be provided in	Study intervention will be provided in HDPE bottles. Each	Study intervention will be provided in HDPE bottles. Each

Study Intervention(s)				
	wallet will be labeled as required per country requirement. Products will be provided with blinded labels.	blister wallets. Each wallet will be labeled as required per country requirement. Products will be provided with blinded labels.	bottle will be labeled as required per country requirement. Products will be provided with blinded labels.	bottle will be labeled as required per country requirement. Products will be provided with blinded labels.
Current/Former Name(s) or Alias(es)	PF-07321332	NA	ritonavir	NA

Study Arm(s)			
Arm Title	Nirmatrelvir/ritonavir 5-day	Nirmatrelvir/ritonavir 10-day	Nirmatrelvir/ritonavir 15-day
Arm Type	Experimental, placebo	Experimental, placebo	Experimental
Arm Description	Participants will receive nirmatrelvir/ritonavir 300 mg/100 mg (or 150 mg/100 mg for participants with eGFR $\geq 30$ to $< 60$ mL/min/1.73 m  or eCrCl $\geq 30$ to $< 60$ mL/min) q12h from Day 1 through Day 5 followed by placebo for nirmatrelvir/placebo for ritonavir q12h for Day 6 through Day 15.	Participants will receive nirmatrelvir/ritonavir 300 mg/100 mg (or 150 mg/100 mg for participants with eGFR $\geq 30$ to $< 60$ mL/min/1.73 m  or eCrCl $\geq 30$ to $< 60$ mL/min) q12h from Day 1 through Day 10 followed by placebo for nirmatrelvir/placebo for ritonavir q12h for Day 11 through Day 15.	Participants will receive nirmatrelvir/ritonavir 300 mg/100 mg (or 150 mg/100 mg for participants with eGFR $\geq 30$ to $< 60$ mL/min/1.73 m  or eCrCl $\geq 30$ to $< 60$ mL/min) q12h from Day 1 through Day 15.
Associated Intervention Labels	Nirmatrelvir/ritonavir (5-day)	Nirmatrelvir/ritonavir (10-day)	Nirmatrelvir/ritonavir (15-day)

Nirmatrelvir/ritonavir may be shipped by courier to study participants if permitted by local regulations and in accordance with storage and transportation requirements for the nirmatrelvir/ritonavir. Pfizer does not permit the shipment of nirmatrelvir/ritonavir by mail. The tracking record of shipments, including temperature monitoring data, and the chain of custody of nirmatrelvir/ritonavir must be kept in the participant's source documents/medical records.

### 6.1.1. Administration

The first dose of study intervention will be administered at the site.

Nirmatrelvir 150 mg tablets or placebo for nirmatrelvir will be administered with ritonavir 100 mg or placebo for ritonavir capsules for 15 days. Participants will be dispensed 1 blister wallet card of nirmatrelvir 150 mg tablets and 1 bottle of ritonavir capsules at the Day 1 site visit. Participants will be dispensed 1 blister wallet card of nirmatrelvir 150 mg or placebo for nirmatrelvir tablets and 1 bottle of ritonavir capsules or placebo for ritonavir at the subsequent Day 5 and Day 10 visits. Participants will be instructed to take:

- 2 tablets of nirmatrelvir 150 mg or placebo for nirmatrelvir q12h;
- 1 capsule of ritonavir 100 mg or placebo for ritonavir q12h.
  - Participants with moderate renal impairment (eGFR  $\geq 30$  to  $< 60$  mL/min/1.73 m^2 or eCrCl  $\geq 30$  to  $< 60$  mL/min at screening) will receive either 1 tablet of nirmatrelvir 150 mg and placebo for nirmatrelvir or 2 tablets of placebo for nirmatrelvir (Section 6.6). The dose for ritonavir remains unchanged (ie, participants will receive 1 capsule of ritonavir 100 mg or placebo for ritonavir q12h).

Participants should take the first dose of study intervention on Day 1, during the in-person visit; that is, participants should take 2 tablets of nirmatrelvir 150 mg and 1 capsule of ritonavir 100 mg at the same time and no more than 15 minutes apart. The study intervention should be taken every 12 hours ( $\pm 4$  hours), but no more than twice in a calendar day. Timing of the second dose of nirmatrelvir/ritonavir may be adjusted slightly to allow participants to select a convenient 12-hour dosing schedule as long as the second dose is taken at least 4 hours but no later than 16 hours after the first dose. Once the dosing schedule is adjusted, subsequent doses should be taken every 12 hours ( $\pm 4$  hours).

If a dose is delayed, it should be taken as soon as possible, but no later than 4 hours before the next scheduled dose, and then resume the normal dosing schedule. If the participant misses a dose by more than 8 hours, the participant should not take the missed dose and instead take the next dose at the regularly scheduled time. The participant should not double the dose to make up for a missed dose. Dosing should be stopped at the end of the treatment period (30 doses total). Any remaining tablets and/or capsules at the Day 5, Day 10, and Day 15 visits should be returned.

Participants will swallow the study intervention whole and will not manipulate or chew the study intervention prior to swallowing. Participants may take the study intervention with or without food. Taking study intervention with food may improve tolerability. Refer to the IPM for additional dosing and administration instructions.

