**Table 1. Study Schedule of Assessment**

Visit Identifier' Abbreviations used in this table may be found in Section 10.11.	Screening	Baseline (Day 1)	Day 5	Day 10	Day 15	Day 21	Day 28	Day 35	Day 44	LTF/U		ET (pilot to Day 44)	Notes
										Week 12	Week 24		
Visit Window	Day -1 to Day 1	0 days	bl:1 day	bl:1 day	±2 days	±2 days	±2 days	±3 days	±3 days	±1 days	±7 days	±5 days	
 
Screening procedures may be done from Day -1 to Day 1, and may be completed on the same calendar day as Baseline/Day 1 procedures. If screening and baseline visits are conducted on the same calendar day, assessments and procedures that are listed to occur at both visits only need to be completed once.
 

Study intervention dispensation		X	X	X									
 
Study intervention will be dispensed on Day 1, Day 5, and Day 10 (see Section 6.1.1).
 
Should eGFR or eCrCl (based on the point-of-care creatinine) on Day 5 or Day 10 warrant a dose modification, replacement study intervention will be dispensed on Day 5 or Day 10. See Section 10.7.1 for age specific kidney function calculations.
 
See Section 6.6.
 

Study intervention administration		Day 1 through Day 15											
 
Baseline assessments should be performed before administration of the first study intervention, except for PK sampling.
 
The first dose of study intervention will be administered to all participants on Day 1 during the in person visit. All subsequent doses of study intervention (ie, 29) will be self-administered (or administered to the participant by a legal guardian or caregiver). If only 1 dose of study intervention is administered on Day 1, study intervention administration should end on Day 16.
 
See Section 6.1.1.
 

Study Intervention Accountability													
Retrieval of unused study intervention and empty study intervention containers			X	X	X							X	
 
If the Day 15 visit is conducted prior to last dose of study intervention, empty study intervention containers and unused study intervention should be returned at the Day 21 visit.
 
See Section 6.5.
 

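### Unused drug is collected at the Day 5 and Day 10 visits with no deferral, so read literally an on-schedule visit can swap the last active dose for placebo in the 5- and 10-day arms

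*Protocol*

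**What the plan says.** - **Arms (Protocol 6.1).** The 5-day arm takes active drug "q12h from Day 1 through Day 5 followed by placebo for nirmatrelvir/placebo for ritonavir q12h for Day 6 through Day 15". The 10-day arm is active through Day 10 and on placebo from Day 11. The 15-day arm is active throughout.
- **Supply (Protocol 6.1.1).** The switch is made by what is dispensed: a new nirmatrelvir wallet and "1 bottle of ritonavir capsules or placebo for ritonavir at the subsequent Day 5 and Day 10 visits". Both visits have a window of ±1 day (Schedule of Activities).
- **Return (Protocol 6.1.1).** "Any remaining tablets and/or capsules at the Day 5, Day 10, and Day 15 visits should be returned". The retrieval row of the Schedule of Activities is marked at the same three visits. Sections 6.2 and 6.3 bar redispensing of returned drug.
- **Deferral (Schedule of Activities).** "If the Day 15 visit is conducted prior to last dose of study intervention", the return moves to the Day 21 visit. There is no matching note for Day 5 or Day 10, and Section 6.1.1 contains no deferral at all.
- **Dose count.** The course is 30 doses, with at most two in a calendar day (6.1.1). The Schedule of Activities adds: "If only 1 dose of study intervention is administered on Day 1, study intervention administration should end on Day 16".
- **Containers (Protocol 6.2.1).** Bottles and cards come back at the next visit where appropriate. The section gives no rule for doses not yet due.

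**The concern.** The last active dose of the 5-day course is dose 10, and of the 10-day course dose 20. A visit on the scheduled day can come before that dose. If the participant hands over what is left and cannot have it back, the next dose comes from the new supply. That supply is placebo at Day 5 in the 5-day arm and at Day 10 in the 10-day arm.

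Treatment duration is the only randomized difference in this trial. Under the literal rule, the duration delivered depends on the day and hour of the visit. No deviation is needed for this to happen, only a visit between the morning and evening doses. Site staff are blinded (6.4.2), so they cannot see that a return has cost an active dose. The sponsor dealt with the same situation at Day 15, but not at the two visits where the product can change.

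**Working it through.** **The plan's own figure.** 15 days × 2 doses = 30. The Schedule of Activities gives 1 dose at the site plus 29 later doses, which is also 30. The stated total is reproduced.

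**When the last active dose falls due.** With two doses on Day 1, five days × 2 = 10, so dose 10 is the second dose of Day 5, and dose 20 is the second dose of Day 10. With one dose on Day 1, 1 + 2 × 4 = 9 doses are taken by the end of Day 5. Dose 10 is then the first dose of Day 6, and dose 20 the first dose of Day 11.

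**Doses taken before a visit.** Let f be the doses on Day 1 (1 or 2), d the visit day, and s the doses already taken on the visit day. Then

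doses taken = f + 2 × (d − 2) + s.

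For a visit between the two daily doses, s = 1. Under the literal rule, everything after that visit comes from the new supply.

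| Visit days | Doses on Day 1 | 5-day arm, active | 10-day arm, active |
|---|---|---|---|
| 5 / 10 | 2 | 2 + 2×3 + 1 = 9 of 10 | 2 + 2×8 + 1 = 19 of 20 |
| 5 / 10 | 1 | 1 + 2×3 + 1 = 8 of 10 | 1 + 2×8 + 1 = 18 of 20 |
| 4 / 9 | 2 | 2 + 2×2 + 1 = 7 of 10 | 2 + 2×7 + 1 = 17 of 20 |
| 6 / 11 | 2 | dose 10 already taken, none lost | dose 20 already taken, none lost |

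The share of the active course lost in the first row is 1/10 = 10% and 1/20 = 5%. In the third row it is 3/10 = 30% and 3/20 = 15%. The counts assume that each supply holds at least 10 doses; the pack size is not stated.

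**Which visit causes the loss.** An early return at Day 5 takes no active drug from the 10- or 15-day arm at that point, because their next supply is also active. The loss arises at Day 5 in the 5-day arm and at Day 10 in the 10-day arm. In the 15-day arm there is no swap to placebo, and any shortfall depends on the unstated pack size.

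**Would the planned summary show it?** SAP 6.4.3 divides doses received by doses planned over the whole treatment period, so active and placebo doses are pooled. Take 30 planned doses and the 5-day participant with 9 active doses. With 10-dose packs, (9 + 10 + 10)/30 = 29/30 = 97%. With 11 or more per pack, the last supply makes up the missing dose and the result is 30/30 = 100%. Either way the participant counts as compliant.

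**The case against.** The strongest reply is that the literal reading is not the natural one. The return sentence follows directly on the instruction to stop after 30 doses, so what remains could mean surplus after the scheduled doses. The arm definitions are explicit, and a site that took back the Day 5 evening dose would contradict them. Section 6.1.1 also says: "Refer to the IPM for additional dosing and administration instructions". The IPM may settle the matter.

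Much of this stands. It shows what was intended, but it does not resolve the wording: Section 6.1.1 names the Day 5 and Day 10 visits, and the only written exception is for Day 15.

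The loss is also not automatic. Dosing is every 12 hours ±4 hours, so dose 10 may be taken as early as 8 hours after dose 9, and Section 6.5 provides for doses taken at the site. With two doses on Day 1, an afternoon visit can therefore include dose 10 before the return. This does not help when one dose was taken on Day 1, because the limit of two doses per calendar day puts dose 10 on Day 6.

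Any shortfall would be traceable through pill counts, timed diaries and container numbers (6.2.1, 6.5). It is recorded even though the planned summary does not separate it.

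A reader might try to infer the pack size from the limit of more than 115% compliance in Section 6.5, on the view that such overuse requires surplus doses. The documents state neither the denominator nor equal packs, so they do not support that inference.

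**Conclusion.** The point holds as a conflict between the return instruction and the randomized regimens. Followed literally, visits on the nominal day between doses give 9 of 10 and 19 of 20 active doses in the 5- and 10-day arms. The figures are 8 of 10 and 18 of 20 with one dose on Day 1, and 7 of 10 and 17 of 20 at Day 4 and Day 9 visits with two doses on Day 1. They rest on the visit falling between doses, on the next dose not being taken before the return, on supplies of at least 10 doses, and on the IPM not saying otherwise.

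A reader might go further and infer that doses were lost, or that the comparison of durations is biased. The documents support neither. They contain no dosing data, no direction of bias between arms follows from the rule, and the analysis is descriptive with no hypothesis test (Protocol 9.1). The sample size and its precision table are unaffected. Severity is minor.

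**What to change.** Extend the Day 15 deferral to Day 5 and Day 10, and state it in Section 6.1.1 as well as in the Schedule of Activities:

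- Scheduled doses 1–10 come from the Day 1 supply, 11–20 from the Day 5 supply and 21–30 from the Day 10 supply. A missed dose still uses its number. Each supply must hold at least 10 doses.
- Each supply, with any surplus, is returned at the first visit after its last scheduled dose. Same-visit return stays in force when renal function requires a dose change or stop (6.6, 7.1).
- Visits are timed so that the new supply is in hand before dose 11 or 21 is more than 8 hours late. Section 6.1.1 allows a delayed dose "no later than 4 hours before the next scheduled dose", and 12 − 4 = 8 hours.
- Optionally, the SAP reports active doses received by arm beside overall compliance, from container numbers and diary times.

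Dose numbers work better than an instruction to finish the pack: a 12-dose pack, for example, would give the 5-day arm 12 active doses. The rule does not guarantee the full planned course in every case. If a Day 6 or Day 11 visit comes more than 8 hours after dose 11 or 21 was due, that dose is skipped.

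The cost is a wording clarification, a notice to sites and for the IPM, and at most one summary line from data already collected. The downside is that accountability for some containers is delayed by one visit and participants briefly hold two supplies, so labels showing which to use first are needed. If the IPM already contains this rule, a citation in Section 6.1.1 is enough.
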